14.3 Serious Adverse Events

14.3.1 Serious Adverse Event Reporting Procedures

Any AE that meets the criteria for seriousness (Table 4) will be recorded as such within the eCRF. All initial and follow-up SAE reports must be reported by the investigator to PPD Pharmacovigilance Department within 24 hours of the first awareness of the event/information by recording all relevant SAE information in the CRFs of the Medidata RAVE project database. In the event of that Medidata Rave is not available, the investigator should utilise the back-up paper SAE report form to report the Initial SAE or follow-up information within 24 hours. See Emergency Contact Information in Section 3. The SAE Form needs to be transmitted to the PPD Pharmacovigilance Department. The CRF of the Medidata RAVE must be updated as soon as it is available. Applicable fax numbers and email addresses can be found on the form.

14.3.2 Serious Adverse Event Collection Timeframe

The time-period for reporting SAEs will be from the time the ICF is signed by a participant until completion of the study. This includes events occurring during the screening phase of the study, regardless of whether FLT201 is administered.

In addition, any SAE(s) considered “related” to the FLT201 and discovered by the investigator at any interval after the study has completed must be reported to PPD Pharmacovigilance Department, see Emergency Contact Information in Section 3.

14.3.3 Serious Adverse Event NIMP Causality Assessment

As per Section 14.2.4, the investigator must make the assessment of causal relationship for any SAE to the NIMP that the participant has received.

14.3.4 Follow-up of Serious Adverse Events

All SAEs must be followed to conclusion regardless of whether the participant is still participating in the study. Conclusion can be that the event has resolved or until, in the opinion of the investigator, the event has stabilised or been determined to be chronic. The follow-up must be documented in the source document(s).

14.3.5 Serious Adverse Event Onset and Resolution Dates

The onset date of the SAE is defined as the date the event meets serious criteria. The resolution date is the date the event no longer meets serious criteria, the date the symptoms resolve, or the event is considered chronic. In the case of hospitalisations, the hospital admission and discharge dates are considered the onset and resolution dates, respectively.

In addition, any signs or symptoms experienced by the participant after signing the ICF or leading up to the onset date of the SAE, or following the resolution of the SAE, must be recorded as an AE, if appropriate.

14.3.6 Documentation and Reporting of Serious Adverse Events

As well as the expedited reporting noted in Section 14.3.1, SAEs should be captured on the appropriate AE pages in the eCRF and in source document(s).

14.3.7 Fatal Outcome

Any SAE that results in the participant’s death (i.e., the SAE was noted as the primary cause of death) must have fatal checked as an outcome with the date of death recorded as the resolution date. For all other events ongoing at the time of death that did not contribute to the participant’s death, the outcome should be considered not resolved, without a resolution date recorded.

14.3.8 Other Important Medical Events

For this study the following will be considered as important medical events and will be reported in line with SAE reporting procedures.

- Development of a malignancy.
- Development of suspected anti-GCase neutralising antibodies defined as a positive result from the central laboratory in conjunction with a drop in GCase activity levels. (The investigator should contact the Medical Monitor if there is a suspicion of anti-GCase neutralising antibodies [see Section 13.6 for further details].)
- A participant develops a severe allergic reaction related to administration of FLT201.

14.3.9 Pregnancy

If a female participant becomes pregnant the pregnancy should be immediately reported on a pregnancy reporting form and submitted to the PPD Pharmacovigilance Department (Section 3). Progression of the pregnancy and the eventual outcome must be documented on the

pregnancy reporting form. Every reasonable attempt should be made to follow the health of the child for 30 days after birth.

If the female partner of a male participant becomes pregnant before the results from three consecutive semen (or serum, if semen not provided) samples taken at separate visits (at least 1 week apart) after FLT201 administration are negative, consent to report information regarding the pregnancy must be obtained from the participant's pregnant partner. A study-specific pregnancy monitoring information sheet and ICF for partners of study participants must be used for this purpose. If consent is given, the pregnancy should be reported on a pregnancy reporting form and submitted to the PPD Pharmacovigilance Department (Section 3). The site team will request for permission to keep in touch with the participant's partner to follow-up the pregnancy to its conclusion. The PPD Pharmacovigilance Department must be kept informed of any new developments involving the pregnancy.

A pregnancy becomes an SAE in the following circumstances:

- Miscarriage
- Termination (elective or spontaneous)
- Ectopic pregnancy
- Foetal demise
- Congenital anomalies or any birth defect

Such additional SAEs must be reported using the SAE form and should be reported to the Sponsor immediately.

14.3.10 Expedited Reporting of Other Safety Events

New events related to the conduct of the study or the development of the FLT201 which are likely to affect the safety of the participants should be reported according to the existing timelines for expedited reporting.

This includes:

- SAEs which could be associated with the study procedures and which could require modification of the conduct of the study.
- Events which pose significant hazard to the participant population.
- SAEs related to mandatory concomitant medication, product application process (surgical or other) and product failure (including lack of efficacy) should all be considered.
- Events (as described above) which are fatal or life-threatening, will be notified to the IEC/IRB and competent authority by the Sponsor/CRO within 7 days of the Sponsor/CRO learning of them. Events falling into one of the other categories of serious (Table 4) will be reported by the Sponsor/CRO to the IECs/IRBs and competent authority within 15 days after the Sponsor/CRO has learned of them.

Expedited reporting and reporting of AEs will be in accordance with EudraLex Volume 10, Chapter II (Detailed Guidance on the collection, verification and presentation of AE/adverse reaction reports arising from clinical trials on medicinal products for human use ('CT-3'; 2011/C 172/01), June 2011) in the EU and with 21 Code of Federal Regulation Part 312 to the Food and Drug Administration.

Should an event also be considered as an urgent safety measure, it must be reported in line with the requirements set out in Section 14.4.

14.4 Urgent Safety Measures

Urgent safety measures can be put in place by the Sponsor with immediate effect without needing to gain prior authorisation by the IEC/IRB (and competent authority where applicable), to protect clinical study participants from any immediate hazard to their health and safety. The IEC/IRB and national competent authorities will be notified of the new event(s), the measures taken, and the plan for further action as soon as possible.

Implementation of urgent safety measures by the investigator should be notified immediately to the Sponsor.

15 Statistical Analysis

A Statistical Analysis Plan (SAP) will be written and finalised prior to database lock. This plan will give a detailed description of all summaries and analyses that will be presented. All study data will be listed and all relevant data will be tabulated and summarised by cohort/dose level and overall, where applicable. Statistical analysis will be performed using SAS® (SAS Institute Inc., Cary, NC, United States of America) statistical software (Release 9.4 or later). Continuous variables will be summarised using number of observations, mean and standard deviation, median, minimum, and maximum values. Categorical values will be summarised using number of observations and percentages. Any deviations from the analyses planned in the protocol will be detailed in the SAP, and deviations from the original statistical plan will be captured in the clinical study report. Analyses will be reported separately by each study part and, where appropriate, combined (e.g., for safety data).

15.1 Demography and Baseline Characteristics

Baseline parameters and demography (e.g., age, gender, ethnicity) will be summarised. Gaucher disease history, ERT/SRT history, and medical history will be summarised using number of observations and percentages of participants reporting each category. Exposure to investigational product (i.e., total amount of study drug received) will be listed for all participants by cohort/dose level.

15.2 Definition of Analysis Sets

Safety Population: The safety analysis set will include all participants who received any dose of FLT201. This population will be used to report both Part 1 and 2.

15.3 Analysis of Primary Safety Endpoints

Dose-limiting Toxicities

All DLTs will be summarised by cohort/dose level.

Although the dose escalation is based on an algorithm, the final data may be used, for example, to model the DLTs as a function of dose, adjusted for any potential confounders, to further refine any estimate of the MTD (e.g., to determine the probability of toxicity closest to a given threshold toxicity at some observed dose level). The uncertainty around the estimate of the true DLT rate may be provided in terms of 95% confidence intervals or 95% credible intervals.

Adverse Events

Frequency of treatment-emergent AEs and SAEs will be calculated for each body system and preferred term, and by dose level, for number of events and number of participants reporting the event. The severity of the AEs and the relationship to study medication will be summarised for each body system and preferred term by cohort/dose level.

Other Safety Endpoints

Safety endpoints including the following will be summarized descriptively by cohort/dose level.

- Change from baseline in laboratory data
- Change from baseline in 12-lead ECG data
- Change from baseline in physical examination data
- Change from baseline in vital signs data.

15.4 Analysis of Secondary Endpoints

Efficacy

The following secondary efficacy endpoints will be summarised by cohort/dose level.

- Change from baseline to each assessment point in lyso-Gb1 in plasma.
- Change from baseline to each assessment point in spleen volume by MRI.
- Change from baseline to each assessment point in liver volume by MRI.
- Change from baseline to each assessment point in haemoglobin.
- Change from baseline to each assessment point in platelet count.

Pharmacokinetic

Change from baseline in plasma and leukocyte GCase activity will be summarised by cohort/dose level and plotted by participant and overall. The area under curve (AUC) of GCase activity will be calculated from baseline to Week 38 and summarised. The details of derivations of the AUC using a linear trapezoidal rule will be provided in the SAP.

Shedding

Clearance of vg in plasma, saliva, urine, stool, and semen will be summarised by cohort/dose level.

Immune Response to Transgene Product

Immune response to the GCase transgene product measured as change from baseline in total anti-GCase antibody titre and neutralising antibody titre will be summarised by cohort/dose level and plotted.

15.5 Exploratory Endpoints

Efficacy

The following exploratory efficacy endpoints will be summarised by cohort/dose level:

- Change from baseline to each assessment point in bone marrow burden score measured by MRI.
- Change from baseline to each assessment point in bone mineral density measured by DEXA.
 - Z-score and T-score in the lumbar spine (L1-4) and hip (femoral neck).
- Change from baseline to each assessment point in Gaucher disease severity measured by GD-DS3.
- Change from baseline to each assessment point in fatigue measured by FACIT-Fatigue.
- Change from baseline to each assessment point in pain measured by BPI-SF.
- Change from baseline to each assessment point in Gaucher disease activity biomarkers: chitotriosidase, CCL18.
- Change from baseline in bone biomarkers: bsALP, osteocalcin.
- Change from baseline to each assessment point in lung disease measured by chest x-ray and pulmonary function tests.

Pharmacokinetic

AUC, peak, and steady state plasma and leukocyte GCase activity levels will be summarised for each participant and cohort/dose level, as appropriate.

Change from baseline in GCase concentration (antigen levels) will be summarised by cohort/dose level and plotted for each participant and overall.

Steady state may be determined using a model-based approach to determine the slope and whether it is statistically zero. The dose-response relationship will be characterised, using a model-based approach, as appropriate.

Immune Response to AAVS3 Capsid

Immune response to AAVS3 capsid (AAVS3 antibody titre and T-cell response) will be summarised by cohort/dose level.

Change from baseline to each assessment point in immune response biomarkers will be summarised by cohort/dose level.

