A minimum of 4 weeks of safety/tolerability (including DLT), PK, PD, and clinical data will be assessed before dosing each participant (both within a dose cohort and before escalating to the next dose level). Four weeks post-dose approximates the time when leukocyte and plasma GCase activity levels are predicted to achieve steady state, giving an early indication of likely risk:benefit for participants at a given dose level. Any acute dose-limiting toxicities (DLT) may thus be adequately assessed in the 4 weeks post-dose period. A DLT is defined as any severe adverse event (AE) at least possibly related to FLT201 except for increases in alanine aminotransferase (ALT) or aspartate aminotransferase (AST) that are not associated with increases in bilirubin.

Dose escalation will be overseen by a DMC in accordance with the following rules:

1. Safety Assessment Based on DLT

- If 1 participant experiences a DLT, that cohort will be expanded to 3 participants.
- If 2 out of 3 participants in the same cohort experiences a DLT, the DMC will be convened to consider a dose reduction. The DLT rate is expected to be $\leq 33\%$.

2. GCase Expression

If GCase activity is below the normal range (e.g., $<1.5 \mu\text{mol/L/h}$) in the first participant in the cohort and no DLT is observed, dose escalation to the next dose cohort will occur after this first participant to avoid treating the next participant with a dose predicted to be below the therapeutic range.

3. Safety Rules Based on NOAEL

The highest dose that may be tested will not exceed 1.5×10^{13} vg/kg, which is below the no observed adverse effect level (NOAEL) of the FLT201 Good Laboratory Practice (GLP) murine toxicology study (2.57×10^{13} vg/kg).

Primary Objective	Primary Endpoints
To assess the safety and tolerability of a single IV administration of FLT201 in adults with Gaucher disease type 1 (previously treated and previously untreated)	
Primary safety endpoint:
 
 incidence of TEAEs (including DLTs) from Day 1 to the last follow-up visit 
Other safety endpoints:
 
 incidence of AEs, SAEs, and changes from baseline in vital signs, 12-lead ECG, physical examination, and laboratory assessments from Day 1 to the last follow-up
Secondary Objectives	Secondary Endpoints

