PK	To characterize the pharmacokinetics of FLT201	
 • AUC, peak, and steady state GCase activity levels in plasma and leukocytes (baseline to Week 38) • Change from baseline to each assessment point in GCase concentration (antigen levels) • Dose response relationship
Immunologic	To describe the immune response to AAVS3 capsid proteins	
 • Immune response to AAVS3 capsid (AAVS3 antibody titre and T-cell response) • Change from baseline to each assessment point in immune response biomarkers
HRQoL	To assess the impact of FLT201 on HRQoL	Change from baseline to each assessment point in HRQoL measured by SF-36

Abbreviations: AE=adverse event; AUC=area under curve; DLT=Dose-limiting toxicity; HRQoL=health-related quality of life; PK=pharmacokinetic, MRI=magnetic resonance imaging; SAE=serious adverse event; TEAE=treatment-emergent adverse event.

8 Study Design

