15.8 Interim Analysis

On completion of Part 1, an interim analysis will be conducted to inform the decision to start a registrational study. Analysis of 3 months of data from the final participant in Part 1 and longer-term data (up to several years in the follow-up study) in prior participants will enable assessment of durability, adverse events, and clinical parameters that may change over a longer period, such as lung function and bone disease. Planned interim analyses will be detailed in the SAP.

16 Data Management

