### **10.2. Plasma, Leukocyte, Dried Blood Spot GCase Activity**

Sample collections that have an actual sampling time that deviates from the predefined collection time windows will be flagged in the data listings.

The following visit windows will be applied for the GCase sample collections:

Screening: +/-1 week

Weeks 1 to 12: +/-1 day

Weeks 14, 16, 20, 24, 28, 32, 38: +/-3 days

Week 38: +/-1 weeks

Individual GCase activity levels will be presented in data listings. A summary statistic for observed and changes from baseline values will be presented by study part, matrix, cohort, and overall.

Individual GCase raw activity levels will be plotted by-participant over time.

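### Protocol 15.5 lets GCase steady state be inferred from a non-significant slope, with no margin or precision requirement, and the SAP supplies no other criterion

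*Protocol*

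**What the plan says.** Protocol section 7 (Table 3) lists steady-state GCase activity in plasma and leukocytes, from baseline to Week 38, as an exploratory pharmacokinetic endpoint. SAP Table 2-3 keeps it.

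Protocol 15.5 says how it will be reported: "AUC, peak, and steady state plasma and leukocyte GCase activity levels will be summarised for each participant and cohort/dose level, as appropriate". It then gives the one criterion found in either document: "Steady state may be determined using a model-based approach to determine the slope and whether it is statistically zero". The wording is permissive. It fixes no model, time window, significance level, level of analysis (participant or cohort) or tolerance around zero.

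The SAP adds nothing on this point. Section 10.3 derives Cmax, Tmax and AUClast only. Section 10.4 fits a power model to Cmax and AUClast. Section 14, which lists changes from the planned analysis, does not mention steady state.

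**The concern.** A plateau is an equivalence claim: the slope is close enough to zero to be ignored. A test that fails to reject a zero slope does not support that claim, because it also fails when the data are too few or too noisy. The criterion therefore rewards imprecision. It can also fail in the other direction, when a very precise profile is refused the label because of a trivial drift.

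The question is central to this product. Protocol 6.5.1 and 6.5.3.3 rest its value on lasting enzyme production after one infusion, and 6.5.3.1 names loss of GCase expression as a risk. At stake is a misleading statement about durability in the study report.

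**Working it through.** The documents state no error rate for this test, so there is no planned figure to reproduce. The check asks how often a real decline would pass as a zero slope.

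**Inputs from the documents**
- Sampling: SAP 10.2 gives "Weeks 1 to 12: +/-1 day" and "Weeks 14, 16, 20, 24, 28, 32, 38: +/-3 days", with weekly visits up to Week 12 in Protocol Table 1. That is 12 + 7 = 19 scheduled samples from Week 1.
- Earliest start of a plateau: the protocol synopsis says "Four weeks post-dose approximates the time when leukocyte and plasma GCase activity levels are predicted to achieve steady state". Weeks 4-38 give 9 + 7 = 16 samples.
- Later starts, chosen here to show the range: Weeks 12-38 give 8 samples and Weeks 16-38 give 6.
- Cohort size: at least 2 participants, and a third may be added (Protocol 8.1).

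**Assumptions not in the documents**
- Two-sided 5% test.
- Log-linear decline of 30% over the window.
- Independent residuals on the log scale, SD σ = 0.2 (a CV of about 20%), varied from 0.10 to 0.40.

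**Formula.** For an ordinary least-squares slope of ln(activity) on week, with window length L and Sxx = Σ(week − mean week)², the noncentrality is |ln 0.7| / L × √Sxx / σ, with n − 2 degrees of freedom. The miss rate is the probability that a noncentral t falls within ± the critical value. Here |ln 0.7| = 0.3567.

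**One participant, σ = 0.2**

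| Window | n | L | Sxx | Noncentrality | Critical t | Missed |
|---|---|---|---|---|---|---|
| Weeks 4-38 | 16 | 34 | 1595 | 0.01049 × 39.94 / 0.2 = 2.095 | 2.145 | 50% |
| Weeks 12-38 | 8 | 26 | 592 | 0.01372 × 24.33 / 0.2 = 1.669 | 2.447 | 71% |
| Weeks 16-38 | 6 | 22 | 323.3 | 0.01621 × 17.98 / 0.2 = 1.458 | 2.776 | 80% |

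**Sensitivity to σ, one participant (missed)**

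| n | 0.10 | 0.15 | 0.20 | 0.30 | 0.40 |
|---|---|---|---|---|---|
| 16 | 3% | 26% | 50% | 74% | 84% |
| 8 | 21% | 54% | 71% | 84% | 89% |
| 6 | 40% | 68% | 80% | 88% | 91% |

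**Other variants at CV 20% (n = 16, 8, 6).** A one-sided 5% test misses 36%, 56% and 66%. A step loss of 30% from Week 28 is missed 48%, 65% and 77% of the time.

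**Pooled cohort.** With a common slope and separate intercepts for k participants, Sxx becomes k × Sxx and the degrees of freedom are kn − k − 1. At σ = 0.2:
- k = 2, n = 16: noncentrality 2.963, 29 df, missed 18%.
- k = 3, n = 16: noncentrality 3.628, 44 df, missed 6%.
- k = 3, n = 8: noncentrality 2.891, 20 df, missed about 21%.

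**The opposite failure.** At a CV of 5% with 16 samples, a drift of only 10% over the window would be declared non-zero about 64% of the time.

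**What an interval would show.** At σ = 0.2 with 8 samples, the 95% half-width for the log change over Weeks 12-38 in one participant is 2.447 × 0.2 × 26 / √592 = 0.523. An estimate of exactly no change would then carry an interval of −41% to +69%. For three pooled participants it is 2.086 × 0.2 × 26 / √1776 = 0.257, or −23% to +29%. The slope test conceals this difference in information; the interval shows it.

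**The case against.** The strongest reply is that the sentence may never be applied. Its wording is permissive, the SAP contains no slope test, the endpoint is exploratory and all analysis is described as descriptive (SAP 4.2). A decline would not be hidden either: SAP 10.2 provides individual listings, change-from-baseline summaries and by-participant plots of raw activity. This limits the consequence, and it stands. It does not supply a criterion. The endpoint remains in SAP Table 2-3, and the protocol sentence is the only guidance for anyone who has to report it.

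A second reply is that the miss rates depend on assumed inputs. That also stands. With σ of 0.10 to 0.15 and 16 samples, or with pooled cohorts and 16 samples at σ = 0.2, most 30% falls would be detected. The logical flaw needs no assumed σ; its size does.

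Three stronger readings are tempting, and the documents do not support them:
- **That the plan declares steady state by this test and would usually call a 30% loss stable.** The protocol only permits the test, and whether a loss is usually missed depends on unstated variability.
- **That the resulting level feeds the dose-response assessment.** SAP 10.4 uses Cmax and AUClast only.
- **That the interim analysis depends on it.** Protocol 15.8 says the interim data "will enable assessment of durability, adverse events, and clinical parameters", but mentions no slope test, and SAP section 14 says the interim analysis will not be performed.

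The rules for withdrawing or resuming ERT/SRT (Protocol 8.1 and 11.3.1) do not use this test either.

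**Conclusion.** The point holds as a defect in the criterion for an exploratory endpoint. Protocol 15.5 allows absence of a detected trend to stand for a plateau, and the SAP keeps the endpoint without defining it. Under the stated assumptions (30% log-linear fall, two-sided 5%, residual log-SD 0.2), one participant's decline would be missed about 50% to 80% of the time, depending on whether 16 or 6 samples are used. Across the log-SDs tried, from 0.10 to 0.40, the range runs from 3% to 91%. Pooling three participants at SD 0.2 brings it to about 6% with 16 samples and 21% with 8. No dosing or treatment decision in the documents depends on the result, so the consequence is confined to how durability is described.

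**What to change.** 1. Remove the statistically-zero criterion from Protocol 15.5.
2. In SAP 10.3, fix a post-rise window (for example Weeks 12-38) and estimate the slope of log GCase activity over it. Report it as percent change over the window with a confidence interval, per participant and pooled per cohort. Say whether raw or baseline-adjusted activity is used: SAP 10.1 sets negative adjusted values to 0, which have no logarithm.
3. Use the term steady state only if the interval lies inside a margin fixed before database lock, preferably at cohort level. Otherwise report stability not shown.
4. If the analysis is not wanted, list steady state as dropped in SAP section 14.

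This needs a few sentences and a few lines of code, and no new data. The cost is real. With a 90% interval and an illustrative 30% margin (log change between ln 0.7 and −ln 0.7), a true 30% fall would be called a plateau at most about 5% of the time. At a CV of 20%, however, only about 31% (16 samples), 11% (8) and 7% (6) of truly flat single profiles would be confirmed, and a 95% interval would confirm fewer. The estimate with its interval is therefore the main output for individuals, and any steady-state label belongs mainly at cohort level.
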